Aim 2: To determine the impact of sublingual administration of a CBD extract on psychological factors known to influence pain intensity and duration. The investigation of psychological constructs will include evaluating the effects of sublingual administration of a CBD extract on pain-related anxiety, catastrophizing and fear pertaining to participants' views and perceptions toward engaging in strenuous physical exercise, sustaining a musculoskeletal injury and prolonged symptomatic and functional recovery. We hypothesize that the anxiolytic effects of sublingual administration of a CBD extract will diminish the threat and perceived physical stress of exercise-induced pain, physical harm, and prolonged symptomatic and functional recovery.

This exploratory study will provide preliminary data needed to support the hypotheses of a planned larger scale application. Preliminary data will help in better designing a future study aimed at identifying an efficacious dose range of hemp-derived CBD extract, as well as determining the cellular and molecular mechanisms that contribute to symptom resolution and recovery. Our findings may also be helpful for making future improvements for treating a broader range of inflammatory conditions that afflict the musculoskeletal system.

6. Research Plan:

Study Location & Design

The project will involve one study center located on the campus of the University of Florida. Data collection for the study will take place in the Sports Medicine & Human Performance Research Laboratory ([name]). The study protocol will be submitted to the UF Gainesville Health Science Center Institutional Review Board (IRB-01) located in the Gainesville Health Science Center ([name]).

The design will be a double-blind, randomized, vehicle-controlled, three-arm trial. Participants will be randomly assigned to either an active CBD dose group (n=15) or vehicle-control (placebo) group (n=15).. The effects of the active CBD dose groups will be compared to the vehicle-control. Subjects will be required to complete a 15-day study trial spanning a presupplement baseline visit, a controlled daily dosage regimen, pre-exercise baseline testing, eccentric exercise to induce muscle damage, and planned follow-up post-exercise data collection time points.

Study Population

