Safety monitoring will occur during the initial baseline visit as well as throughout the participant's duration in the study, including a 1-week follow-up contact after study termination. As noted below, the baseline assessment conducted during the first visit will include a brief physical exam (including vital signs) and a thorough medical and psychiatric history, including a review of past medical history, concomitant medications, inclusion/exclusion criteria, and potential contraindications. Safety monitoring will include active and passive surveillance procedures using pre-existing safety monitoring guidelines. Participants will be assessed actively at each laboratory visit by study personnel using the side effects/adverse events checklist. Each participant will be read each side effect/adverse event from the checklist and instructed to selfreport as yes (go) or no (no go). If a participant experiences any of the side effects/adverse events from the checklist provided at the baseline visit, study personnel will then contact the study physician ([name]) for consultation and guidance. The side effects/adverse events will be triaged as mild, moderate or severe, and a determination will be made by the study physician as to whether the side effect/adverse event is due to the investigational test article or some other circumstance (e.g. food poisoning). If the reaction or event is determined to be due to the investigational test article and graded moderate to severe by the study physician, the participant will then be instructed to stop participation and advised to seek medical care by their primary physician or hospital. (Refer to stopping criteria below). In the event that emergency care needs to be provided the participant is instructed to immediately call 911 or seek care at a medical health facility (e.g. hospital). The study physician ([name]) would also be contacted for guidance as well. Any serious adverse reaction or event will be followed until full resolution. All adverse reactions and events will be reported to the UF IRB within 24-48-hrs and documented in the participant's file (redcap).

Stopping criteria:

- 1. The PI/physician decides that the participant should be withdrawn for **safety reasons** (presence of active lesions in the oral cavity/sublingual region or suffering side effects or adverse events associated with the use of the investigational product).
 - a. List of side effects and adverse reactions are listed below*

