- 2. Participant is unwilling to continue in the study.
- 3. Lack of compliance with protocol.
- 4. Investigator or study sponsor stops the study for any reason.
- 5. Participant becomes pregnant.
- 6. Participant is enrolled in error or lost to follow-up (lost to follow-up will be defined as a subject failing to attend planned study visits or failure to respond to contacts by study personnel after documented 2 attempts).

*Potential Side Effects and/or Adverse Events (AEs):

- Feelings of anxiety (nervousness, restlessness or being tense, feelings of danger, panic, or dread), paranoia, or negative mood (depression or suicidal thoughts), or paranoia.
- 2. Poor quality of sleep (persistent insomnia).
- 3. Feelings of extreme fatigue, sleepiness or drowsiness.
- 4. Feelings of nausea (upset stomach, vomiting or gastro-intestinal (GI) distress (e.g. diarrhea).
- 5. Change in or loss of appetite.
- 6. Feelings of light-headedness or dizziness.
- 7. Visual disturbances such as blurry/double vision or dilated pupils.
- 8. Hypotension, hypertension, tachycardia, heart palpitations, syncope or dyspnea.
- 9. Development of a skin rash with redness and itching.
- 10. Loss of muscle coordination (clumsiness)
- 11. Muscle spasms

Visit 1 (Consenting, screening, randomization and test product distribution, Day 1)

Participants will be consented. Consenting will be performed by one of the co-investigators in a private room. The following procedures will be performed: urine sample for pregnancy (females) and toxicology screen (presence of cannabinoids), a brief physical exam (including vital signs: measurements for height, weight, pulse, blood pressure and body temperature), obtaining a thorough medical and psychiatric history, including a review of past medical history, concomitant medications, inclusion/exclusion criteria and potential contraindications, assessment of the oral cavity and sublingual area to rule out any active lesions or abnormalities (bleeding, sores, ulcers, abscesses, etc.). If any lesions are found to be present, the research assistant will document the findings and follow up with a consultation phone call with the study physician to determine next steps. The study participant may choose to be excluded from participation or wait until the condition fully resolves. If the participant continues with the study protocol, follow up oral assessments will be repeated at visits 2 through 6.

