Results of urine screening for pregnancy and toxicology (presence of cannabinoids) will be available and assessed during the first visit. If the urine test (pregnancy or cannabinoids) comes back positive, the participant will be excluded from the study. The participant will complete several psychological questionnaires (FPQ-9, PCS, PASS-20, PSQI, & LEFS), followed by tests for muscle soreness and quantitative sensory testing (QST). Each participant will be provided a detailed safety monitoring checklist of side effects and/or adverse reactions that they may potentially experience from ingesting the investigational product. Participants will then be instructed on how to perform their own passive surveillance for identifying these side effects/adverse events and what to do if they experience any of them between study visits while they are ingesting the investigational test article (Days 1 through 10). Participants will be instructed to maintain current activity levels and not to initiate a resistance-training or weightloss program for the duration of the study. Participants will then be randomly assigned to an experimental group and instructed on how to ingest the investigational test article (or placebo) and dosing procedures, which will be dispensed in a quantity to last for the next 15 days. Each participant will be provided a daily log chart to record their daily CBD doses for compliance and monitoring purposes. A pre-exercise visit will be scheduled. Each subject will receive \$10 for completion of the test session.

During the passive surveillance period (Days 1 through 10) participants will be instructed to contact the PI ([name]) if they experience any of the side effects/adverse events from the checklist provided at the baseline visit. [name]/[name] will then contact the study physician ([name]) for consultation. The side effects/adverse reactions will be triaged as mild, moderate or severe, and a determination will be made as to whether the side effect/adverse reaction is due to the investigational product or some other circumstance (e.g. food poisoning). If the event is determined to be due to the investigational test article and graded moderate to severe by the study physician, the participant will then be instructed to stop participation and seek medical care by their primary physician or hospital. Any participant that reports a serious adverse event will be followed to full resolution.

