Participants will be informed during the consenting period, both in writing on the consent form and verbally, that participants will likely experience soreness and stiffness within the exercised muscles after completing the exercise protocol. We postulate that participants will likely experience some level of heightened fear and anxiety (pain-related or other) in the 10-day wash-in phase of the investigational test article before they undergo the experimental exercise protocol and recovery phase. We feel this will be quantifiable on the self-reported psychological questionnaires that the participants will complete before and after the experimental protocol.

Data Management & Analysis

All information and data collected will be stored in locked filing cabinets or in computers with security passwords and accessed only by members of the research team. This process facilitates

data entry and collection, allows for participants to complete self-report questionnaires, and offers optimal security for collecting research-related information. The proposed Data Management will be housed within the Human Performance Laboratory and a secure webbased platform approved by UF (e.g. Redcap) will be used.

Outcome measures will be analyzed using a two-way ANOVA with repeated measures (between-group; within-time) or distribution free test (e.g Friedmans) as indicated by data distribution. Statistical significance will be set at p<0.05. If significant interactions occur, the Tukey post-hoc test will be used to reveal where the differences occur. We will calculate effect sizes and estimates of precision for all outcomes. All data analyses will be performed using SPSS® for Windows 16.0 (SPSS, Inc., Chicago, IL).

A **Data and Safety Monitoring Plan** will consist of two components: (1) overseeing participant safety and data monitoring, and (2) performance of monitoring. Since this project is viewed as low potential risk, all key personnel will perform all data and safety monitoring on an as needed basis.

7. Possible Benefits:

There is no known direct benefit from participating in this study. Study participants have the option of being paid for their time performing research related duties or they may choose to receive extra credit for a course they are currently taking and that may or may not be considered a benefit. There are no other obvious benefits to the study participant.

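### Anxiety is both an Aim 2 outcome and a listed stopping event, and anyone stopped for it by Day 11 has no on-treatment FPQ-9 or PASS-20 score

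*Combined protocol and SAP*

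**What the plan says.** All references are to the combined protocol and SAP.

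- **Outcome.** Aim 2 (section 5) covers "evaluating the effects of sublingual administration of a CBD extract on pain-related anxiety, catastrophizing and fear". Secondary Outcome Measures names the FPQ-9, PCS and PASS-20, and Primary Outcome Measures adds a VAS for anxiety and fear. Sleep quality is measured by the PSQI but is not part of Aim 2.
- **Listed event.** The list of potential side effects and adverse events begins with "Feelings of anxiety (nervousness, restlessness or being tense, feelings of danger, panic, or dread". Its second item is "Poor quality of sleep (persistent insomnia". Stopping criterion 1 refers to this list and allows withdrawal of a participant "suffering side effects or adverse events associated with the use of the investigational product".
- **Gate.** Safety Monitoring sends each reported event to the study physician. The stop instruction applies "If the reaction or event is determined to be due to the investigational test article and graded moderate to severe by the study physician". Visit 1 repeats this for Days 1 to 10, and the consequence there is that "the participant will then be instructed to stop participation and seek medical care by their primary physician or hospital".
- **Expectation.** The end of Secondary Outcome Measures says "participants will likely experience some level of heightened fear and anxiety (pain-related or other) in the 10-day wash-in phase".
- **Timing.** FPQ-9 and PASS-20 are taken on Days 1, 11 and 15. The Day 1 set precedes randomisation. At Visit 2 (Day 11) the checklist is read first, and questionnaires follow only for those who go on.
- **Analysis.** Data Management & Analysis specifies a two-way repeated-measures ANOVA or a distribution-free test. It names no analysis population, missing-data method or assessment at exit.

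**The concern.** The symptom that Aim 2 tries to reduce can also remove a participant before it is next measured. The protocol expects anxiety to rise in the same ten days in which participants are told to report it. Assignment is blinded, and the protocol gives no criteria for telling product-related anxiety from worry about a disclosed painful bout. Its only example of another cause is food poisoning.

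A severity gate tends to select participants with high anxiety, so missingness can depend on the outcome. If the product works, the vehicle arm would lose more anxious participants and the benefit would look smaller. If the product provokes anxiety, the active arm would lose more and the harm would look smaller. With 15 per arm, one or two people carry weight, and an exit score that is not taken at the time cannot be recovered.

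**Working it through.** **Step 1: the route to a missing score.**

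1. Anxiety is an outcome (Aim 2) and a listed event (criterion 1).
2. A report on Days 1 to 10, or at the Day 11 checklist, leads to physician triage.
3. If the event is attributed to the product and graded moderate to severe, participation ends, not only dosing. Criterion 1 also permits withdrawal for product-associated events and states no severity threshold.
4. The Day 11 questionnaires come after the checklist and only for those who continue. A person stopped by then has the Day 1 FPQ-9 and PASS-20 and nothing on treatment.
5. A repeated-measures ANOVA that needs complete records drops that person.

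**Step 2: size and direction.** The plan gives no SD, effect size, power or dropout figure, so there is no figure of its own to reproduce. From the documents: 15 per arm. Assumed for illustration:

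- Anxiety is normal with SD 1, with mean 0 on vehicle and −d on active.
- Anyone above the cut c that marks the top share q of the vehicle arm is withdrawn with probability a, under the same rule in both arms.

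Write φ for the normal density, u = c + d, and q′ for the share of the active arm above c. Then:

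- vehicle completer mean = −aφ(c)/(1 − aq)
- active completer mean = −d − aφ(u)/(1 − aq′)
- completer difference (vehicle minus active) = d + aφ(u)/(1 − aq′) − aφ(c)/(1 − aq)

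With a true benefit of d = 0.5:

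| q | a | Expected loss of 15, vehicle / active | Calculation | Difference (SD) |
|---|---|---|---|---|
| 0.05 | 0.25 | 0.19 / 0.06 | 0.5 + 0.010 − 0.026 | 0.48 |
| 0.10 | 0.50 | 0.75 / 0.28 | 0.5 + 0.042 − 0.092 | 0.45 |
| 0.20 | 1.00 | 3.00 / 1.35 | 0.5 + 0.178 − 0.350 | 0.33 |

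For the last row, c = 0.842, φ(c) = 0.280 and 0.280/0.8 = 0.350; u = 1.342, φ(u) = 0.162, q′ = 0.090 and 0.162/0.910 = 0.178. Over the grid of q = 0.05, 0.10, 0.20 and a = 0.25, 0.50, 1.00, the range is 0.33 to 0.48 SD. A simulation with 2,000,000 draws per arm agrees.

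With a true harm of 0.5 SD (d = −0.5), the apparent harm runs from 0.47 SD (q = 0.05, a = 0.25: −0.5 + 0.053 − 0.026 = −0.473) down to 0.26 SD (q = 0.20, a = 1: −0.5 + 0.594 − 0.350 = −0.256).

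With d = 0 the two correction terms are equal and cancel, so this mechanism alone does not create a difference where none exists.

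**Step 3: context.** The standard error of a 15 v 15 difference is √(2/15) = 0.37 SD. The difference detectable with 80% power at two-sided 0.05 is (1.960 + 0.842) × 0.365 = 1.02 SD. The bias in the benefit grid, 0.02 to 0.17 SD, is below half of one standard error.

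**The case against.** The strongest case against is that a symptom may properly be both an outcome and an adverse event, and that the gate protects the trial. A mandatory stop needs two findings by a physician who has the psychiatric history on file and may name another cause. Mild nerves about the bout need not lead to a stop. The risk section calls the chance of the side effects it describes minimal and does not name anxiety among them. The study is exploratory, and the bias is toward no difference. All of this stands, and it lowers the likely number of stops. It does not remove the route: there are no attribution criteria, criterion 1 has no severity threshold, and nothing is measured at exit.

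A reader might infer more than the documents support:

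- **That everyone will be anxious, or that anxiety alone is enough to stop.** The text says some level is likely, and the mandatory stop is gated.
- **That sleep raises the same problem for Aim 2.** The sleep item is narrowed to persistent insomnia, and Aim 2 does not include sleep.
- **That the bias is about 0.23 SD.** That follows from removing exactly the two highest scorers from one arm only: the expected top two of 15 normal scores are 1.736 and 1.248, and (1.736 + 1.248)/13 = 0.23. The gate acts on grade and attribution rather than on the score, and it applies to both arms.
- **That the listed feelings are what the questionnaires measure.** The list extends to panic and paranoia, while FPQ-9 and PASS-20 concern pain. They overlap but are not identical.

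**Conclusion.** The concern holds in a limited form. The plan lets withdrawal depend on an Aim 2 outcome, schedules no on-treatment FPQ-9 or PASS-20 for anyone stopped by the Day 11 checklist, and has no analysis for the resulting gap. A complete-case analysis would tend to understate a benefit or a harm. Under the assumed rates, a true 0.5 SD benefit would appear as 0.33 to 0.48 SD and a 0.5 SD harm as 0.26 to 0.47 SD.

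These sizes rest on normal scores, the same rule in both arms, withdrawal that follows the score, and rates chosen for illustration. A looser link between score and stopping would make the bias smaller. If there are no such stops, there is no bias from this source. The documents do not allow the number to be estimated. The change is still worth making before enrolment because it is cheap and the lost scores cannot be obtained later.

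**What to change.** 1. **Reconcile the text.** The event list, the Safety Monitoring and Visit 1 stop instructions, criterion 1 and the prediction of wash-in anxiety must be made consistent on how expected anticipatory anxiety is handled. The clinical rule is for the investigators, and no change to the safety decision is proposed.
2. **Measure at exit.** Give the existing anxiety/fear VAS, FPQ-9, PASS-20 and PCS to anyone stopped, when able and willing, and add the PSQI after a sleep event. On Day 11, take them before a checklist-based exit takes effect where this does not delay care.
3. **Analyse everyone randomised.** Use a mixed model on all available scores. Add a sensitivity analysis for informative withdrawal that draws on the exit score rather than simply carrying it into Day 11. An exit score is taken off-schedule, possibly at the height of an event, and only in those stopped.
4. **Report.** Tabulate anxiety-related stops by arm beside the Aim 2 result, and sleep-related stops separately.

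Cost: about ten minutes of existing questionnaires for the few people stopped, some off-schedule scores that need careful handling (the one-month recall of the PSQI limits what it adds), and one extra table.

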Current research has shown evidence that phytocannabinoids may have a promising therapeutic potential in a variety of physical and psychological ailments, and cannabidiol (CBD) is of particular interest due to its positive safety profile, non-intoxicating effects and widespread capabilities in a number of musculoskeletal diseases. Three primary reasons people consume CBD on a global basis, in addition to the fact that it is non-intoxicating, are for symptomatic (pain) relief, anxiety reduction, and improved sleep quality. Very little is known about CBD and how it functions in the body from both an efficacy and mechanistic perspective, especially in humans. There is a large consumer base for this product that will be expanding exponentially in the next few years. Most of the evidence available is anecdotal from the personal testimony of consumers. We aim to determine the efficacy of a controlled short-term trial of CBD ingestion for reducing symptomatic response and facilitating recovery following induced muscle injury. We will assess, in serial fashion, symptomatic response, functional limitations and recovery of the quadriceps muscle following induced injury in which selected doses of CBD oil will be delivered using a sublingual route of administration during a 15-day pre-injury consumption and post-injury recovery phase. A double-blind, randomized, two-arm study design will be used and participants will be randomly assigned to either an active dose (n=15) or vehicle control group (n=15). Our clinical outcomes include measures of muscular pain and disability along with measures of pain-related fear and anxiety. Our laboratory-based study design is desirable and advantageous because it is a controlled method of tracking individuals using an experimental model of injury that is translatable to clinical populations. Another advantage of this study design is that it will address, in parallel fashion, two of the primary reasons people are consuming CBD - symptomatic relief and anxiety reduction. This exploratory study will provide preliminary data needed to support the hypotheses of a planned larger scale application.

4. Background:

Overview and Rationale for Study

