We will be able to study important bio-behavioral factors in a concomitant manner that are specific to the central tenets of ingesting a hemp-extract that contains CBD and other minor cannabinoids. Biological factors to be studied include clinical signs of reduced symptomatology and functional limitations as well as quicker recovery to baseline that are indicative of anti-inflammatory and analgesic effects of CBD ingestion. Additional prior work by our group shows robust associations among pain intensity and measures of negative affect. Thus, we will also be able to study pain-related fear-avoidant and anxiety behaviors that are involved in the participants' perception of the threat or anticipation of a painful experience related to intense exercise and injury before, during and after undergoing our experimental injury model.

5. Specific Aims of Study:

Our overall objective is to generate preliminary data in humans on the effects of ingesting a hemp-extract investigational product that contains CBD for reducing pain-related anxiety and symptoms related to induced muscle injury. We aim to determine the efficacy of a controlled short-term trial of hemp-derived CBD ingestion for reducing symptomatic response and facilitating recovery following induced muscle injury. We will assess, in serial fashion, symptomatic response (both physical and psychological factors), functional limitations and recovery of the quadriceps muscle following induced injury in which selected doses of a hemp-derived CBD oil will be administered orally during a 15-day pre-injury consumption and post-injury recovery phase. We will evaluate these responses with an experimental repeated-measure design spanning pre-treatment, baseline measurement, injury induction, short-term sublingual administration of a hemp-derived CBD extract (or placebo) and recovery.

Aim 1: To determine time-related patterns of symptomatic and functional recovery in response to sublingual administration of either a low-dose or a high-dose CBD extract after muscle injury. Based on the purported anti-inflammatory, analgesic, and anxiolytic effects of CBD ingestion, we hypothesize that short-term sublingual administration of a hemp-derived CBD extract will limit the symptomatic response and functional limitations after induced muscle injury allowing for an expedient recovery to baseline conditions.

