Inclusion Criteria: a) male and female adults between the ages of 18-35 years and b) English speaking, and c) both female and male subjects must be currently practicing acceptable methods of birth control, such as abstinence, and methods of contraception (barriers, oral, patch or other prophylactic methods).

Exclusion Criteria: (a) use of cannabis products on a regular basis OR positive urine test for cannabis, (b) history of seizure disorder (self or family), traumatic brain injury, liver, kidney, or cardiovascular disease, (c) current medical condition that would prevent the participant from performing strenuous resistance exercise, (d) weight lifting for the lower extremities (legs) more than twice a week, (e) currently experiencing pain in the hips, leg, or knee region, (f) pregnancy, lactating or positive urine pregnancy test, (g) known allergy to CBD, coconut/sesame oil, or tree nuts (coconut).

If the participant self-reports that they are currently using tobacco products or a nutritional/dietary supplement, or if they take prescription anti-depressant/anxiety medications, the participant may continue to use the product(s) but they must be on a stable dose at least 3 months prior to randomization as well as during the 15-day study trial period. Also, if the participant is currently using OTC anti-inflammatory medication (e.g., Advil, Aleve, Aspirin) on a regular basis, we will ask that they stop taking the medication at least 7 days before randomization and refrain from using the product during their participation in the study trial.

Investigational Product & Dosing Schedule

Participants will be provided a 30mL bottle with a syringe dropper on day 1 with instructions to ingest the solution orally using a sublingual route of administration (0.5 cc ~1/2 dropper) twice per day (BID) 12 hours apart (morning and evening) at the prescribed daily dosages: Vehicle-control (0mg/30mL hemp extract = no hemp extract), and active Dose (2000mg/30mL hemp extract = 67mg/day). The sublingual route of administration allows the product to be absorbed directly into venous circulation, and thus bypasses the liver and eliminates the consequences of first pass metabolism; ultimately increasing its bio-availability. The bioavailability of CBD administered orally (including sublingual) is estimated to be 13-19% and its half-life estimated to be around 18-32 hours. 35,36

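### The Days 1–10 limit on self-surveillance and on contacting the PI is shorter than dosing (to Day 15) and safety follow-up (to about Day 22): a minor gap, fixable by wording

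*Combined protocol and SAP*

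**What the plan says.** All references are to the combined protocol and SAP.

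**The ten-day limit.** Section 6, Visit 1, applies it twice. In the first paragraph participants learn to monitor themselves and what to do "if they experience any of them between study visits while they are ingesting the investigational test article (Days 1 through 10"). The next paragraph repeats the range for reporting: "During the passive surveillance period (Days 1 through 10) participants will be instructed to contact the PI".

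**Dosing.** The same Visit 1 paragraph has product handed out "which will be dispensed in a quantity to last for the next 15 days". The opening summary describes CBD oil "delivered using a sublingual route of administration during a 15-day pre-injury consumption and post-injury recovery phase", and section 5 (Specific Aims) says that it "will be administered orally during a 15-day pre-injury consumption and post-injury recovery phase". Study Location & Design adds: "Subjects will be required to complete a 15-day study trial spanning a presupplement baseline visit, a controlled daily dosage regimen". Investigational Product & Dosing Schedule gives a twice-daily regimen but names no last dosing day.

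**Safety follow-up.** Safety Monitoring and Stopping Criteria states that monitoring covers the participant's "duration in the study, including a 1-week follow-up contact after study termination", by active and passive surveillance. It also contains an instruction, without a day limit, to call 911 or go to a medical facility in an emergency. From Visit 2 on, staff read out the checklist and take vital signs at each visit. After Visit 6 there is one safety call a week later, which covers both past and current checklist events.

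**The concern.** The Visit 1 text defines the self-surveillance window by a criterion (off site, between visits, taking product) and then attaches a day range that satisfies it only in part. Participants are also off site and still dosing in the intervals between the Day 11 to Day 15 visits, just after the induced injury. The contact instruction inherits the same range, and nothing later in the available text extends it.

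What is at stake is how soon the study physician hears of an event. The checklist includes items that may fall short of an emergency but should be reported promptly, such as palpitations, dizziness, visual disturbance and low mood. During dosing, the decision to stop a participant for a product-related event graded moderate to severe depends on someone reporting it. After dosing, the issue is only how early an event is reported and followed up.

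**Working it through.** There is no sample-size or error-rate figure to reproduce here; the check is calendar arithmetic.

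**Inputs**
- Visit 1 on Day 1; Visit 2 (exercise bout) on Day 11; Visits 3, 4 and 5 on Days 12, 13 and 14; Visit 6 at 96 hours after exercise (visit headings, section 6).
- Safety call 1 week after completion (paragraph after Visit 6). Completion is taken to be Visit 6.
- Dosing every 12 hours, half-life 18–32 hours (Investigational Product & Dosing Schedule).

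**Reproducing the plan's calendar**
- Visit 6 = Day 11 + 96/24 = Day 15, which agrees with the heading.
- Call = Day 15 + 7 = about Day 22.

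**What Days 1–10 corresponds to**
- Visit 1 to Visit 2 = 11 − 1 = 10 days. The range is therefore the first between-visit interval. It is also what the paragraph before Data Management & Analysis calls the 10-day wash-in.
- Intended dosing is 15 days, so as a label for ingestion the range is 15 − 10 = 5 days short.

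**Reporting routes in the available text, by period**

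| Period | Scheduled staff check | Instruction to contact the PI | Longest wait for a non-emergency report |
|---|---|---|---|
| Visit 1 to Visit 2 (Days 1–10) | none between the visits | yes | none; participant can report at once |
| Visit 2 to Visit 6 (Days 11–15) | every day (5 visits, 4 intervals) | not stated | about 24 hours |
| Visit 6 to call (Day 15 to about Day 22) | the call itself | not stated | about 7 days |

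The emergency instruction applies in all three rows.

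**Exposure in the two later periods**
- Days 11–15: doses between consecutive daily visits = 24/12 = 2. No dosing day in this period lacks a visit (0 of 5).
- After Visit 6: the plan gives the half-life as "its half-life estimated to be around 18-32 hours". Five half-lives are 5 × 18 = 90 hours (3.8 days) to 5 × 32 = 160 hours (6.7 days), against 7 × 24 = 168 hours to the call. If the last dose is taken around Visit 6 (an assumption, since the plan does not say), most of the remaining product clears before the call. Exposure is therefore falling in the same week that has no stated non-emergency route.

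**The case against.** The strongest reply is that the range is deliberate. Days 1–10 is the only multi-day interval between visits during dosing, and the plan itself calls it the passive surveillance period. From Day 11 passive surveillance gives way to something closer: a daily visit with every checklist item read aloud. The emergency instruction has no day limit, and the closing call asks about events that have already happened. This largely stands, and it is why the gap on Days 11–15 amounts to about a day's delay at most.

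Three stronger readings are tempting, and the documents do not support them.

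- *Dosing stops on Day 10.* A reader might infer this from the parenthesis. The 15-day supply in the same paragraph, the opening summary and section 5 all point to Day 15. The range is misplaced; it is not a stopping day.
- *More than half of follow-up is unmonitored.* A reader might add the 4 days after Visit 2 to the 7 days after Visit 6. That sum mixes days with a staff check every day and days with none before the call, so it should not be used as a measure of the gap.
- *The stopping rule fails in the last week.* If dosing ends around Visit 6, little is left to stop. Only earlier reporting and follow-up are at issue.

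It is also fair to say that the plan promises only the 1-week contact after the last visit, and that participants' actual instructions may be fuller: the consent pages were removed from the copy reviewed, and the Visit 1 checklist handout was not available. The finding is therefore about the protocol text, not about what participants are told. It remains true that the stated window does not meet its own criterion, and that the text leaves the week after Visit 6 without a non-emergency route.

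**Conclusion.** The point holds as a minor one. Self-surveillance and the instruction to contact the PI are limited to Days 1–10, while dosing is intended through Day 15 and safety follow-up runs to about Day 22. The consequence is a possible delay of up to about 24 hours on Days 11–15. In the 7 days after Visit 6, the only stated route before the call is the emergency one. Sample size, power and analysis are not affected.

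This rests on three assumptions: that dosing continues to Day 15 as the summary, aims and supply sentence imply; that the call falls 7 days after Visit 6; and that the unseen participant materials do not already extend the instruction. If they do, only the protocol wording needs to be brought into line. The half-life figures additionally assume a last dose around Visit 6, and the conclusion does not depend on them.

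**What to change.** In section 6, Visit 1:

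1. First paragraph: delete the Days 1–10 parenthesis after the reference to ingesting the product, and state that self-surveillance runs from Day 1 until the 1-week follow-up call. Reword the sentence so that the ingestion phrase no longer bounds the period; otherwise it would carry two windows.
2. Second paragraph: replace the opening reference to a ten-day passive surveillance period with *From Day 1 until the 1-week follow-up call*, ahead of the instruction to contact the PI.
3. Keep the active checks at Visits 2–6 as they are.

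Any matching participant instructions should be aligned. The cost is wording in the protocol and those instructions, and possibly a few more calls from participants. No visits, tests, participants or analyses are added.
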